**Objective :**

1. To compare the oral stereognostic ability of the completely edentulous patient with maxillary tori and patient without maxillary tori.
2. To compare the time duration taken for oral stereognosis of the completely edentulous patients with and without maxillary tori.

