### **Background of the study**

Mantecchini et al (1998) evaluated oral stereognosis in edentulous subjects rehabilitated with complete removable dentures. Stereognosis was evaluated with and without the denture in place. The results showed that the older subjects had poorer stereognostic ability than the younger ones, whereas the duration of edentulism appeared not to influence this ability. The presence of a correct prosthetic rehabilitation appeared to improve stereognostic ability. Subjects with poorer stereognostic ability appeared more satisfied with their rehabilitation than did those with better stereognostic ability.

Pedreira A et al (2004) evaluated oral stereognosis in dentate and edentulous subjects with and without cleft lip and palate before and after chewing. The results demonstrated that oral stereognosis levels of dentate subjects were higher than those observed in edentulous subjects. Oral stereognosis levels of denture wearers with cleft lip and palate were lower than those observed in edentulous subjects without clefts. Chewing did not influence the oral stereognosis levels in edentulous patients.

Meenakshi S et al (2014) evaluated the oral stereognostic ability after rehabilitating patients with complete dentures and concluded that covering the palatal mucosa with a denture does not reduce oral stereognostic ability. Oral stereognostic test is a reliable test to measure patients' oral stereognostic perception which would enable the patient to appreciate the functional limitations of the denture.

Bakhtiyari J et al (2014) evaluated oral stereognostic ability and response time in children with cleft palate and normal children and showed that there was a significant difference between oral stereognosis and response time of children with cleft palate and that of normal

children ( $P < 0.05$ ) The results can be used for developing intervention programs for children with cleft palate in the early years of their lives.

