Jin-Hyuck Park (2016) assessed the changes in oral stereognosis of healthy adults by age. This study investigated oral stereognosis in 184 healthy adults with normal eating and swallowing function. Results showed that oral stereognosis ability differ in age of the subjects and test pieces employed to test the OSA. The younger age group scored higher with short response time comparing to the older age group except for comparison between 20s and 30s age groups suggesting that aging negatively impacts in OSA in terms of speed in which sensory information is responded. Response time was negative correlated with test scores ( $r = -0.956$ ,  $P < 0.001$ ) and these proved that OSA decreases with age.

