#### **Subject**

Inclusion Criteria :

- Complete edentulous patient with maxillary tori and without maxillary tori
- Complete edentulous patient who give consent and is willing to participate

Exclusion Criteria:

[figure not shown]
- Patients with swallow and mastication dysfunction
- Patients with cognitive disturbances
- Uncooperative patients.
- Patients with oral lesions, pathologies and TMJ disorders.

- Patients with systemic diseases
- Patients allergic to acrylic resin

The study group will comprise of 20 completely edentulous patients with maxillary tori and 20 completely edentulous patients without maxillary tori who are willing to participate in this study. The patients who fulfill the above mentioned inclusion and exclusion criteria would be conveniently selected from among outpatients of the SEGi Oral Health Centre. Informed consent will be obtained from each patient following sufficient explanation of purpose and contents of the research.

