#### Assessment of oral stereognostic test

The OSA test will be conducted in Segi Oral Health Centre under quiet condition. All patients will be seated comfortably in upright position on dental chair. All the test pieces will be kept out of sight of patient before and during the test. Test pieces will be placed intraorally and patients will be instructed to identify the shape of test pieces with their tongue and palate. A visual representation chart of all 6 shaped forms will be provided to patient for identification purpose. Patients will be asked to identify the correct shape form by pointing out on the

corresponding shape form on the chart. There will be no trial test held to avoid learning effect. The 6 test pieces will be presented randomly to the patients and correct answer will not be informed to the patients during the OSA.

The duration time for recognition of each shaped form for each patient will be noted and answers will be recorded on an OSA evaluation form. A correct answer will be recorded as one point and incorrect answer is zero point. A full 6 points will be scored if all answers were correct. The response time and the OSA scores will be recorded. The response time will be the time between the placements of test piece in the oral cavity until the identification of the test.

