### **Statistical analysis plan**

The data collection will include the time duration and OSA scores for recognition of each shaped form and the answers recorded on an OSA evaluation form. All data analyses will be conducted using SPSS version 22. Descriptive statistic will be used to analyse the mean and standard deviation of the OSA test scores and the response time for answering. Analysis of variants (ANOVA) will be applied to compare the test scores and response time among the completely edentulous patient with maxillary tori and completely edentulous patient without maxillary tori. Spearman's rank correlation coefficient would be used to investigate the relationship between response time and OSA test score.

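### The planned Spearman correlation of response time with score names neither torus group nor age; read as pooled, it can show a negative relationship that is absent among comparable patients

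*Combined protocol and SAP*

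**What the plan says.** The correlation appears once, in the Statistical analysis plan: "Spearman's rank correlation coefficient would be used to investigate the relationship between response time and OSA test score". No group, covariate or unit of analysis is given. The sentence before it compares both variables between the torus groups by ANOVA, so the plan itself allows that torus status may move either one. The same section lists what is collected: "The data collection will include the time duration and OSA scores for recognition of each shaped form". Age is not in that list, but neither is torus status, so the list is not exhaustive.

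The group mix is set by design (Subject): "The study group will comprise of 20 completely edentulous patients with maxillary tori and 20 completely edentulous patients without maxillary tori". Patients are a convenience sample, and the readable criteria contain no age limit and no matching on age. The score runs from 0 to 6 (Assessment of oral stereognostic test): "A correct answer will be recorded as one point and incorrect answer is zero point".

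On age, the Background section says of a study in healthy adults: "The younger age group scored higher with short response time comparing to the older age group". Of a study in edentulous patients it reports ability only: "older subjects had poorer stereognostic ability than the younger ones". On tori, the Introduction states that no study has examined their effect on oral stereognostic ability.

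The two objectives are "To compare the oral stereognostic ability of the completely edentulous patient with maxillary tori and patient without maxillary tori" and "To compare the time duration taken for oral stereognosis of the completely edentulous patients with and without maxillary tori". The correlation is in neither.

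**The concern.** A factor that makes patients both slower and less accurate produces a negative time-score correlation in a mixed sample, even if the two are unrelated among patients alike on that factor. The plan has two candidates. Torus status is the comparison of interest, and its share of the sample comes from recruitment quotas. Age is reported in the protocol's own literature to act on both time and score.

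A pooled coefficient therefore partly reflects the quota and the age mix. The stake is interpretation: readers may take it to mean that slower patients recognise shapes worse, other things being equal, and the pooled figure alone cannot show that.

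**Working it through.** **No design figure to reproduce.** The plan states no alpha, power or target correlation for this analysis. A two-sided 5% level and complete data are assumed.

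**Inputs from the documents.** n = 40, 20 per group; score 0 to 6, one point per piece.

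**Inputs assumed.** The documents give no size for a torus or age effect. Torus shifts are d SD up in time and d SD down in score. Age correlates +a with time and -a with score and is balanced between groups. Time and score are unrelated given group and age.

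**Step 1, closed form on a continuous scale.** With within-group correlation w and shifts d1, d2 in two equal groups, pooled r = (w + d1·d2/4) / sqrt[(1 + d1²/4)(1 + d2²/4)].
- d = 0.5: -0.0625/1.0625 = -0.059
- d = 0.8: -0.16/1.16 = -0.138

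For age, r = -a²: -0.09 at 0.3 and -0.25 at 0.5.

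**Step 2, simulation on the actual scale.** 40,000 studies per scenario, log-normal time, and four score models: round(3.8 + 1.3z) limited to 0-6, and Binomial(6, expit(0.6 + kz)) with k = 1, 1.5 and 2.

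| Scenario | Mean pooled Spearman | Share p<0.05 |
|---|---|---|
| No shared effect | -0.001 to 0.001 | 5.0-5.1% |
| Torus 0.5 SD, opposite directions | -0.044 to -0.057 | 5.9-6.5% |
| Torus 0.8 SD, opposite directions | -0.104 to -0.136 | 9.9-13.3% |
| Age correlation 0.28 | -0.055 to -0.072 | 6.5-7.4% |
| Age correlation 0.3 | -0.062 to -0.083 | 6.8-8.0% |
| Age correlation 0.5 | -0.174 to -0.229 | 19.4-30.3% |
| 0.8 SD shift in one outcome only (rounded and k = 1 models) | -0.001 to 0.001 | 4.9-5.2% |

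The 0.28 row shows a narrower age range. If age spread is half that of a sample with correlation 0.5, the correlation falls to 0.5·0.5/sqrt(0.75 + 0.25·0.25) = 0.277. The last row shows that a factor acting on one outcome alone creates nothing. In a separate simulation (20,000 studies; rounded, k = 1 and k = 2 models), a 0.8 SD torus shift and an age correlation of 0.5 together gave -0.26 to -0.33, so the two influences accumulate.

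**Step 3, partial coefficient.** Rank time, score and age; regress the time and score ranks on group and age rank; correlate the residuals (df = 40 - 2 - 2 = 36). In the Step 2 scenarios its mean is -0.012 to 0.002, and it is significant in 4.8-5.3%.

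**Step 4, cost when there is no shared effect.** The critical |r| rises from 0.312 (df 38) to 0.320 (df 36). At a conditional correlation of -0.4, simulated power goes from 66.6% to 64.4% (rounded score), and from 42.6% to 40.8%, 52.6% to 50.3% and 57.4% to 55.0% (k = 1, 1.5, 2). The 95% limits around zero are tanh(1.96/sqrt(35)) = ±0.32. A separate coefficient in one group of 20 has tanh(1.96/sqrt(17)) = ±0.44.

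**Step 5, what the partial coefficient misses.** With within-group correlations of -0.5 and +0.5, the mean partial coefficient given group is 0.00.

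**The case against.** The strongest reply is that the plan contains no error. It promises to describe the relationship between two variables and does not say that the relationship holds at fixed age or torus status. The pooled coefficient does what it says, no conclusion or sample size rests on it, and asking for a conditional coefficient substitutes a different target. It is also true that pooling is inferred, that the torus effect is unknown, and that the age evidence on both outcomes comes from healthy adults including people in their 20s and 30s. At 0.5 SD, or with a narrower age range, the distortion is hard to tell from zero with 40 patients.

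Most of this stands and sets the limits of the point. It does not remove it. The plan treats torus status as a possible influence on both variables in one sentence and leaves it out of the next, and its own literature names age as an influence on both. A coefficient that separates these influences is available at almost no cost.

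Stronger readings that a reader might infer are not supported:
- *The test has an inflated false-positive rate.* The shares in the table are detection rates of a real association in the mixed sample, not type I error of the Spearman test.
- *Pooling may equally well hide a relationship.* With same-direction shifts of 0.8 SD and a conditional correlation of -0.4, the pooled value does shrink to -0.14 to -0.18. That requires a group that is slower but more accurate. Nothing in the documents suggests one, and the age evidence points the other way.
- *Age will not be collected.* The list of data is incomplete, so this is a matter to confirm.

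**Conclusion.** The point holds as a cheap improvement. The sentence leaves group and age unspecified and, read naturally, pools all 40 patients. If either factor makes patients both slower and less accurate, the pooled coefficient turns negative without any relationship among patients of the same group and age. Under assumed effects this is minor at 0.5 SD or an age correlation of 0.3, and becomes noticeable at about 0.8 SD or a correlation of 0.5. The result depends on a shared effect on both outcomes, which is reported only indirectly for age in this population and is unknown for tori. The comparisons of score and time between groups do not depend on this coefficient.

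**What to change.** Confirm that age is recorded for each patient, and replace the Spearman sentence in the Statistical analysis plan with:

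> As an exploratory analysis with one pair of values per patient (total score; mean or median response time over the six pieces, chosen in advance), the rank correlation of response time with OSA score will be reported as a partial Spearman coefficient controlling for torus group and age, with a 95% CI, alongside the pooled Spearman coefficient and a scatterplot by torus group.

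The unit is stated because time and score are recorded per piece, and 6 × 40 = 240 piece-level pairs are not independent. A Fisher-z interval with standard error 1/sqrt(n - 5) serves for the CI; it covered zero in 94.6-95.0% of simulated studies under the binomial models when the true conditional correlation was zero.

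The partial coefficient removes only the influence of torus group and of recorded, monotone age. It cannot reveal opposite relationships in the two groups, which is why the scatterplot is included. The cost is at most one data field, slightly more analysis, and about 2 to 3 points of power if there is no shared effect.
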